# 1. INTRODUCTION

## *1.1 Literature Review*

Colorectal cancer is the third and second most common malignancy in male and female patients, respectively, with up to 1.8 million new cases and 860,000 deaths per year [1].

Anterior resection with total mesorectal excision (TME) was first proposed by Heald in 1982 [2] and is currently the gold standard surgical technique for middle and lower rectal cancer. Heald considered that the metastatic spread of the tumor occurs through micro-implantations in the lymph node network of the mesorectum, and much less through horizontal intramural infiltration, and thus defined rectal resection margins at 5cm or even 2cm for well-differentiated neoplasms. Therefore, he suggested that mesorectum displays a greater risk for micro-metastatic disease and should be removed en-bloc with intact resection margins.

Similarly in 2009, Hohenberger proposed the complete mesocolon excision (CME) concept for the treatment of colon cancer, based on the respective embryological development anatomical planes. After analyzing a large cohort of patients, he concluded that this operation type leads to a significant reduction in the local recurrence and an increase in the overall survival rates [3].

Hohenberger proposed open CME as the optimal surgical technique for colon cancer, under the premise that the following principles are met [3]:

- Dissection of Toldt's fascia and mesocolon preservation
- Central vascular ligation
- Extensive locoregional lymph node dissection

CME technique, as described by Hohenberger in 2008, is an extension of Heald's TME and it is based on the sharp dissection and separation of the visceral fascia that surrounds the colon from the parietal fascia. The aim is to fully mobilize the colon and the corresponding mesocolon, which is surrounded bilaterally by sheets of visceral fascia. This ensures the complete resection of the tumor and the corresponding lymph nodes. At the same time, central vascular ligation allows the dissection of the apical lymph nodes [3].

There are three resection planes: the mesocolic, intramesocolic and muscularis propria plane. The ideal resection plane is the mesocolic, in which the colon is removed, along with the entire mesocolon and all the venous and lymphatic tissue, without violating the visceral fascia [4]. Surgical specimens categorized into either of the other two resection planes are associated with reduced R0 resection rates [6] and with reduced overall survival. Characteristically, the muscularis propria resection plane has been associated with up to 15% reduced survival rate compared to the mesocolic plane [7, 8].

There are specific morphometric characteristics of surgical specimens that are used to assess their quality. These include tumor and proximal colon high vascular ligation distance, number of lymph nodes, length of resected small bowel and colon, and total area of the mesocolon [7, 8]. These characteristics are directly related to the number of harvested lymph nodes and, therefore, to overall survival [7, 8].

According to initial results, CME specimens were larger in size, contained a longer length of colon, a larger mesenteric surface and a greater number of lymph nodes compared to the standard colectomy specimens [3]. In addition, a greater distance of the tumor from the resection margins was highlighted [3]. Specifically for right colon cancers, recent publications [6–8, 11–14] have shown that CME can achieve better morphometric specimen characteristics and a greater number of lymph nodes. In a recent randomized study, Di Buono et al. [15] compared the completion of CME or not, during laparoscopic right colectomy. A significant difference was found in favor of CME, regarding the specimen length and the lymph node harvest.

Despite these, the literature evidence regarding the morphological and qualitative characteristics of laparoscopic and open CME specimens are still inconclusive. Specifically for right colectomies, in the comparative study by Gouvas et al. [6], it was observed that the percentage of the mesocolic resection level was 100% in open colectomy, in contrast to 85.7% in the laparoscopic approach. However, this difference was not statistically significant. In a retrospective study by Ali Koc et al. [17], no difference was found between open and laparoscopic CME in terms of specimen length, R0 resection rate and number of resected lymph nodes. A recent

publication by Ali Zedan et al. [18], argued that open CME is associated with longer specimens, larger mesenteric area, and increased resection margins. Another interesting finding was that the number of lymph nodes and the distance of the ligation site were greater in the laparoscopic CME group. However, the meta-analysis by Anania et al. [19] failed to validate any difference between the two methods in the total number of lymph nodes. Finally, a comparative analysis of our own series of patients did not show superiority of one technique over the other in terms of resection level, specimen length and number of lymph nodes [20].

Additional qualitative characteristics of a colon cancer operation include operative time, intraoperative blood loss, time of bowel function recovery, length of postoperative hospital stay, postoperative complications, as well as overall survival and local recurrence rate [2, 6, 8–10]. In a recent meta-analysis by Anania et al. [16] applying the principles of CME to right colectomies did not affect the rates of postoperative leaks, bleeding, overall complications, and reoperations. However, CME right colectomy was associated with optimal results in terms of 3-year overall survival and 5-year disease-free survival [16].

Regarding the application of laparoscopy principles to CME colectomies, previous studies [6–8, 11–14] have confirmed that it is a technique with optimal results, such as faster postoperative recovery, shorter hospital stay, and lower morbidity. There is agreement between studies regarding the perioperative benefits of laparoscopic CME right colectomy versus the open method. According to Huang et al. [21], the length of operative time between the two techniques was comparable. Laparoscopic right colectomy was associated with significantly lower intraoperative blood loss and faster initiation of feeding. In addition, these patients were discharged earlier compared to their counterparts in the open colectomy group. Moreover, no differences were observed in complication and local recurrence rates [21]. These findings were also confirmed by the comparative study of Sheng et al. [22], where the application of the minimally invasive technique resulted in lower levels of postoperative pain, and faster recovery. Accordingly, Shin et al. [23], applying propensity score analysis, to remove possible confounding factors, in a sample of 2249 right colectomies and found that the technique is an independent predictor for 5-year disease-

free survival. Pooled data from Anania et al. [19], confirmed the superiority of laparoscopic CME in the rates of postoperative complications, intraoperative bleeding, and length of hospital stay. These are also in accordance with our own experience, where a significant benefit of the laparoscopic approach was shown in the duration of hospitalization and septic complications, at the cost of prolonged surgical time [20].

## **2. OBJECTIVE**

### *2.1 Description of the proposed project*

The purpose of this research protocol is to compare open versus laparoscopic right colectomy (according to the CME technique of complete mesocolic excision) for right colon cancer. This study will be designed as a prospective randomized controlled trial. The comparison of the two techniques will include endpoints regarding the quality characteristics of the specimens and the oncological results. In addition, the effectiveness of the two methods will be evaluated in terms of the early and late postoperative period.

### **3. MATERIAL AND METHODS**

#### *3.1 Population*

The sample will consist of males and females aged 18 to 90 years.

#### *3.2 Diseases*

The study will include patients with right colon cancer that will be submitted to right colectomy based on the CME principles.

#### *3.3 Inclusion / Exclusion Criteria*

Inclusion criteria are the following:

- Histologically confirmed right colon cancer (cecum, ascending colon, hepatic flexure)
- Surgical resection based on the CME principles
- Patient 18 to 90 years old
- ASA score  $\leq$ III
- T $\leq$ 3
- Elective operation
- Signed informed consent of the patient

Exclusion criteria are the following:

- Non elective operation (hemorrhage, perforation, obstruction)
- Locally advanced disease (T4)
- Distant metastases (Stage IV)
- ASA $\geq$ IV
- Previous laparotomy
- BMI >35 kg/m^2
- Active sepsis or systemic infection
- Untreated physical and mental disability

- Pregnancy or breast-feeding
- Lack of compliance with the protocol process
- Non-granting of signed informed consent

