### *3.9 Calculation of the sample size*

Sample size calculation was based on the primary outcome. According to the literature [6] the percentage of mesocolic plane preservation in open and laparoscopic colectomy is 100% and 85.7%, respectively. Therefore, for  $\alpha=5\%$ , power=80%, 10% dropout rate, and 1:1 allocation ratio, the calculated sample in each group is 57 patients. Therefore, the total sample of the study is 114 patients.

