### *3.10 Randomization*

The randomization of the patients will be performed using a dedicated software with a 1:1 allocation ratio. The allocation group will be concealed with opaque envelopes that will be opened upon entrance of the patient in the operation theatre.

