### *3.11 Blindness*

There will be no blindness at the level of the patient, the treating physicians (surgeon, anesthesiologist) and the researcher who will record the data.

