### *3.13 Monitoring*

Following hospital discharge, the patient will be called for reassessment one month after the operation to evaluate any postoperative complications. At the same time, the pathology report of the specimen and the adjuvant treatment will be recorded. In addition, at 5 years postoperatively, overall, disease-free survival and recurrence rates will be recorded.

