### *3.14 Medication*

Both preoperative and postoperative patient treatment will be standardized. The principles of the ERAS protocols will be applied to patients [23]. More specifically, antimicrobial prophylaxis will include the administration of intravenous antibiotics within 60 minutes prior to the onset of operation. Patients will receive preoperative, mechanical bowel preparation and per-os antimicrobial prophylaxis. Prior to surgery, patients will abstain from solid and liquid foods for 6 and 2 hours, respectively. The nasogastric tube will be removed postoperatively and repositioned only in case of ileus. Postoperative analgesia will include a multidisciplinary approach using analgesics (paracetamol, lornoxicam) in combination with dorsal or epidural analgesia. Opioid administration will be avoided. Postoperative nausea and vomiting prophylaxis will include granisetron 3mg / 3ml IV. Mechanical and pharmaceutical thromboprophylaxis will be used. A zero-balance approach to fluid losses will be applied. Mobilization will be initiated from the first postoperative day. Feeding will be initiated on the basis of the intestinal function recovery.

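### Does the undated non-compliance exclusion in Section 3.3 allow patients to be removed after randomisation?

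*Protocol*

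**What the plan says.** Section 3.3 gives "Lack of compliance with the protocol process" as an exclusion, separate from the bullet on consent that follows it. No time of assessment is attached.

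Other sections place the protocol's steps on both sides of allocation:

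- **Before.** Section 3.14: "Patients will receive preoperative, mechanical bowel preparation and per-os antimicrobial prophylaxis". Preoperative fasting is set in the same section.
- **Allocation.** Section 3.10 conceals the group in "opaque envelopes that will be opened upon entrance of the patient in the operation theatre".
- **After.** Section 3.14: "Mobilization will be initiated from the first postoperative day". Section 3.13: "the patient will be called for reassessment one month after the operation to evaluate any postoperative complications". Outcomes are recorded again at 5 years.

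Section 3.11 states "There will be no blindness at the level of the patient, the treating physicians", and extends this to the researcher who records the data. Section 3.9 plans 57 patients per group with "10% dropout rate, and 1:1 allocation ratio".

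**The concern.** The bullet names non-compliance as a fact, where many protocols would write that the patient is expected to be unable to comply. Taken literally, compliance is seen only once a process is under way, and part of this one runs after everyone knows the arm. If patients were removed for what they did after surgery, removal could depend on treatment. Section 1.1 credits laparoscopic surgery with benefits "such as faster postoperative recovery, shorter hospital stay, and lower morbidity", and recovery bears on early mobilisation. A rule that dropped slow recoverers would then take more patients from one arm than from the other.

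At stake would be the comparability of the arms on bowel recovery, hospital stay and one-month complications. The primary endpoint is the plane of the resected specimen. The protocol does not link it to later patient behaviour, so there the cost would be mainly lost numbers.

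**Working it through.** **1. The neighbouring bullets.** None of the exclusions in Section 3.3 has a time point. Active sepsis and pregnancy are also worded as facts and could also arise after surgery. Sepsis could even differ by arm, since Section 1.1 reports fewer septic complications with laparoscopy in the centre's own series. Nobody would read those bullets as removing randomised patients. Refusal of consent, the next bullet, can only be an entry criterion. If a missing date were a defect, it would be one for the whole list. The section heading supplies the time.

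**2. Whether the bullet needs post-allocation events to have meaning.** It does not. Bowel preparation, oral prophylaxis and fasting are all due before the patient enters theatre, which is when the envelope is opened. Failure to follow them can be observed as a fact while the arm is still concealed.

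**3. The post-allocation steps.** The sentences on mobilisation and on the one-month recall describe what staff will do. Slow mobilisation is already handled as outcome: Section 3.12 makes a steady gait a condition of discharge, and Section 3.8 times hospital stay to meeting the discharge criteria. A patient who mobilises late is counted as a longer stay.

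**4. Other signs of intent.** Section 3.7 codes a failed resection plane as 0, Section 3.8 makes conversion an endpoint, and Section 3.9 plans for 85.7% success in the laparoscopic arm. All three presuppose that patients whose operation departs from the ideal are kept.

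**5. The numbers.** Inputs from Section 3.9: success 100% open and 85.7% laparoscopic, α = 5% (taken as two-sided), power 80%, dropout 10%, 57 per group.

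Plan's own figure, pooled normal formula, mean proportion (1 + 0.857)/2 = 0.9285:

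n = [1.96·√(2 × 0.9285 × 0.0715) + 0.8416·√(0.857 × 0.143)]² / 0.143² = (0.714 + 0.295)² / 0.02045 ≈ 49.8, so 50 per group.

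With dropout: 50/0.9 = 55.6, so 56. The protocol states 57, one more.

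If removals unrelated to outcome used the whole allowance: 57 × 0.9 = 51.3, so 51 remain and 57 − 51 = 6 per arm are lost. That is the evaluable number the plan already provides for. With no failures in the open arm and X ~ Bin(n, 0.143) failures in the laparoscopic arm:

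| Method, two-sided 5% | Power at n = 57 | Power at n = 51 |
|---|---|---|
| Normal-approximation formula | 85% | 81% |
| Pooled z-test, exact, P(X ≥ 4) | 97% | 95% |
| Fisher, exact, P(X ≥ 6) | 84% | 76% |

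Only Fisher's test, which the protocol does not name, falls below 80% at 51. That would be equally true of ordinary dropout and says nothing about this bullet.

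**The case for a change.** The strongest case for the concern is that eligibility wording belongs to the protocol, that staff apply Section 3.3 as written, and that no sentence confines the bullet to the period before the envelope is opened. Section 3.12 does not help, because its exit criteria concern hospital discharge. In an unblinded trial whose planned contrast rests on about eight failures (57 × 0.143 ≈ 8), a loose rule could matter: 0/57 against 8/57 gives Fisher p = 0.006, whereas removing four of those failures gives 0/57 against 4/53 and p = 0.051.

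The textual observation stands: the bullet has no date, and a few added words would make its reading explicit. The inference does not follow. The p-value example needs a surgeon's failure to achieve the plane to be relabelled as the patient's non-compliance, which nothing in the protocol supports. Removals on top of ordinary dropout would cost power (at 48 per arm the formula gives 79%), but the documents neither foresee any nor give a number. How randomised patients who later fail to comply are analysed is a question of analysis sets, which is commonly left to a statistical analysis plan. That plan is not at hand.

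**Conclusion.** The concern does not hold. On the ordinary reading of an eligibility list, the bullet screens patients before allocation and biases no comparison. Harm requires a reading that the protocol nowhere directs and that its endpoint definitions and planning rate speak against. The effect on the primary endpoint is nil, because the only quantified loss is the 10% allowance already in the 57 per group. For the secondary endpoints the documents give no rates, so no figure can be put on them, but no mechanism for removal is laid down either.

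This rests on two assumptions: that Section 3.3 is applied as what its heading says it is, and that the handling of non-compliant randomised patients is settled in the analysis plan. Tying the bullet explicitly to the time before randomisation would be a matter of editorial taste and would correct no error.

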### *3.4 Study Arms*

There will be two study groups in this trial. Patients randomized to the control arm will be submitted to open right colectomy. Accordingly, the experimental study group will undergo laparoscopic right colectomy. Both techniques will adhere to operative principles of complete mesocolic excision (CME).

In the open right colectomy group, the operation will start with a midline incision and dissection based on the lateral to medial approach [6]. The lateral peritoneal fold along Toldt's line will be incised and the ascending colon will be mobilized from the retroperitoneum according to the embryological dissection planes. Dissection will continue until the anterior surface of the superior mesenteric vessels at the third duodenal part. Ileocolic and right colic vessels will be ligated at their origins. For hepatic flexure tumors, the middle colic vessels will be also ligated at their origin [6]. The ileocolic anastomosis will be performed using an automatic stapler. The anastomosis will be completed either with staples or sutures.

In laparoscopic right colectomy subgroup, the patient will be placed in a lithotomy position [21]. Entrance in the peritoneal cavity will be completed via the open Hasson method. With the installation of the pneumoperitoneum (12 mmHg) an exploratory laparoscopy with a 30° optical camera will be performed. Overall, 4 ports will be used: 10mm at the umbilicus for optical entry, 12mm in the left midclavicular line below the umbilicus as the main working port, 5mm at the McBurney point, and 5mm between the umbilicus and the xiphoid process [21]. An incision will be made in the mesenteric peritoneum under the ileocolic vessels [6]. Dissection of the peritoneal fold, under the terminal ileum, will be performed based on the medial to lateral approach. The dissection will continue laterally, below the right paracolic peritoneal fold, and above the pancreas and duodenum, to the conjoined fascias of the lesser epiploic sac. Similar to

the open approach, the ileocolic vessels, as well as the right branches of the middle colic will be ligated at their origin for cecal and proximal ascending tumors. For hepatic flexure cancers, the medial colic vessels will be ligated. Dissection will be completed with the transection of the right gastrocolic ligament, the peritoneum of the right paracolic groove and the peritoneal recess of the terminal ileum. An automatic stapler will be used for the transection of the terminal ileum and the transverse colon. The ileocolic anastomosis will be completed either intracorporeally or extracorporeally, using staples or sutures [6].

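### Section 3.4 names different vessels for ligation in the two arms for the same caecal and proximal ascending tumours, although both arms are meant to follow one CME technique

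*Protocol*

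**What the plan says.** Section 2.1 sets the purpose as a comparison of open and laparoscopic right colectomy, both carried out by CME. Section 3.3 makes the technique an inclusion criterion ("Surgical resection based on the CME principles") and section 3.4 repeats the commitment: "Both techniques will adhere to operative principles of complete mesocolic excision (CME". Section 1.1 lists central vascular ligation among the CME principles but does not list vessels by tumour site. Eligible sites are given in section 3.3: "Histologically confirmed right colon cancer (cecum, ascending colon, hepatic flexure".

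Only section 3.4 names the vessels, and it does so separately for each arm.

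- Open arm, with no limit by site: "Ileocolic and right colic vessels will be ligated at their origins". Then: "For hepatic flexure tumors, the middle colic vessels will be also ligated at their origin".
- Laparoscopic arm, for caecal and proximal ascending tumours, in a sentence that opens by claiming similarity to "the open approach, the ileocolic vessels, as well as the right branches of the middle colic will be ligated at their origin". Then: "For hepatic flexure cancers, the medial colic vessels will be ligated".

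**The concern.** The laparoscopic text announces similarity and then gives a different list. For a caecal or proximal ascending cancer, a surgeon following the open text takes the ileocolic and right colic vessels. A surgeon following the laparoscopic text takes the ileocolic vessels and the right branches of the middle colic.

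The contrast of interest is access, with the CME technique held the same. If the text were followed literally, extent of ligation would travel with access. The protocol itself counts central vascular ligation as part of CME. A difference in the long-term oncological secondary endpoints of section 3.8 (local recurrence, disease-free survival, overall survival) could then not be put down to access alone. Vessel ligation is part of the definition of the intervention, so a statistical analysis plan would not be expected to settle it.

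**Working it through.** No figure in the protocol rests on this text, so the check sets the two arms of section 3.4 side by side.

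**Step 1: the rules as written.** IC = ileocolic, RC = right colic, MC = middle colic, rMC = right branches of the middle colic.

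| Tumour site | Open arm | Laparoscopic arm |
|---|---|---|
| Caecum and proximal ascending | IC + RC, at origin | IC + rMC, at origin |
| Ascending, not proximal | IC + RC, at origin | no separate sentence |
| Hepatic flexure | IC + RC + MC, at origin | vessels called medial colic; level not stated |

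**Step 2: caecal and proximal ascending tumours.** The vessels named in either arm are {IC, RC, rMC}, three groups. The vessels named in both are {IC}, one group. RC is named only for open surgery and rMC only for laparoscopic surgery.

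**Step 3: does the result depend on how the claim of similarity is read?**

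- Reading A, in which the laparoscopic list stands alone: open {IC, RC} against laparoscopic {IC, rMC}. The two arms swap one vessel group for another.
- Reading B, in which similarity carries the open rule over and rMC is added: open {IC, RC} against laparoscopic {IC, RC, rMC}. The laparoscopic arm takes one more group.

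The lists differ on both readings, so the finding for these tumours does not turn on the choice between them.

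**Step 4: the other sites.** Here the reading does matter.

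- Ascending tumours that are not proximal are eligible, because section 3.3 admits the whole ascending colon. Under reading A the laparoscopic text gives them no rule. Under reading B they take the open rule and the arms agree.
- For hepatic flexure tumours, reading A leaves a vessel name that differs from the open text and no stated level. Under reading B the laparoscopic arm takes {IC, RC, MC} at origin and the arms agree.

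**Step 5: is it reconciled elsewhere?** Sections 1.1, 2.1 and 3.3 and the opening of section 3.4 commit both arms to CME. None of them gives a vessel list by site, so they show that the same technique is intended in both arms without saying which list is right.

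**Step 6: reach.** The primary endpoint (section 3.7) is the mesocolic resection plane, yes or no, and is not defined by which vessels are tied. The sample size in section 3.9 uses two plane-preservation proportions (100% and 85.7%), 5% alpha, 80% power, 10% dropout and 1:1 allocation. No ligation quantity enters it, so harmonising the text leaves it unchanged. The protocol gives no mix of tumour sites, so the number of patients affected cannot be derived.

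**The case against.** The strongest reply is that this is loose drafting with no practical effect. Both arms are bound to CME, CME includes central ligation, neither vessel list is said to be exhaustive, and section 3.15 describes the surgeons as past the learning curve. Both descriptions also cite the same comparative study for technique. On this view the word announcing similarity should be given its full effect and the surgeons would do the same operation in either arm.

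Much of this stands. It makes drafting the likely cause, and it disposes of two wider claims that a reader might infer.

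- A reader might infer that the arms disagree at every eligible site. The documents do not support that. For ascending tumours that are not proximal and for the hepatic flexure, the arms agree once similarity is taken to carry the open rule over. The flexure wording (medial for middle, no mention of origin) is a slip that the general CME commitment already covers. Counting the caecum and the proximal ascending colon as two mismatches would also count one sentence twice.
- A reader might infer that patients will in fact receive different ligation, or that recurrence or survival will be altered. Nothing in the protocol shows that taking one of these vessel groups instead of the other changes an outcome.

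The reply does not remove the difference for caecal and proximal ascending tumours. A general commitment to CME does not choose between two explicit lists. Giving similarity its full effect still leaves the right branches of the middle colic named in one arm only. The cited study is not available here, so whether it settles the list is unknown.

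**Conclusion.** The point holds in a limited form and is minor. For caecal and proximal ascending cancers, section 3.4 prescribes different vessels by arm while calling the approaches similar: one of three named vessel groups is shared, and no other section resolves it. Confidence is high that the wording differs. There is no basis for saying that the surgery itself will differ.

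The consequence is conditional. If the text is followed as written, ligation extent is tied to access and the long-term oncological secondary endpoints are harder to attribute to access. No effect size or patient count can be given. It would go too far to infer a bias in the primary endpoint or a fault in the sample size, because neither uses the vessels ligated. The possible gap for ascending tumours that are not proximal, and the wording of the flexure sentence, are secondary points to tidy in the same edit.

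**What to change.** Replace the two ligation texts in section 3.4 with one rule by tumour site that applies to both arms. For example:

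- Caecal and all ascending colon tumours: ileocolic vessels, right colic vessels (where present) and right branches of the middle colic, ligated at origin.
- Hepatic flexure tumours: the same, plus the middle colic vessels at origin.

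Use the term middle colic throughout. Which vessels belong on the list is a surgical decision that the documents cannot settle. The investigators should confirm it, in particular whether the right branches of the middle colic are to be taken for caecal and ascending tumours. Whichever list they choose must be identical in both arms. Access and direction of dissection, which the protocol states openly, remain as planned differences.

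The cost is wording only: no extra patients, procedures or data.
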